#### ***STAGE 2: scanning a/LCI device development***

##### ***Data analysis for Duke site***

The proposed study is designed as a pilot study, intended to provide feasibility and usability data to inform future studies on a larger scale. The planned pilot study will include 10 subjects, which will yield

success/failure metrics of the probe design with 10% precision. Elements of the probe performance that will be evaluated include ease of use by the medical practitioner, patient comfort, ability to access the relevant anatomy, and quality of scanning a/LCI imaging data. Because the goal of the pilot study is the evaluation of general feasibility, no subject data will be excluded if no predetermined exclusion criteria are met.

#### ***Data analysis for Jacobi site***

Data collected from the scanning a/LCI device will include nuclear size and density as a function of depth into the tissue at each “sizing mode” measurement location selected during “mapping mode”. All biopsy samples will be read by Jacobi Pathology per standard clinical care procedure.

To determine sensitivity and specificity for diagnosis of cervical dysplasia, an ROC curve will be created based on the a/LCI data and histological classification. Repeated measures logistic regression models will be used to assess the association of histology with nuclear morphology characteristics after adjusting for other relevant factors. The outcome variable will be dichotomized as “CIN-2 or worse” vs. CIN-1/normal. The predictor will be the morphological nuclear characteristics (nuclear density and diameter at selected depths beneath the tissue surface). Potential confounders will be adjusted for, including age, type of epithelium (i.e. metaplastic, squamous), infections if found, menstrual cycle timing, and sexual behaviors. A compound symmetric correlation matrix will be used to account for the repeated measures within subjects. P-values associated with type I error rates of less than 0.05 will be considered statistically significant in this study. Analyses will be accomplished using JMP Version 9 software (SAS Inst., Cary NC).

One potential problem may be co-registration of a/LCI scan points with biopsy. We will mitigate this risk by using acetowhitening both prior to and after probe application to first guide a/LCI scans to suspicious regions and to return to those points afterwards, as well as using the white light visualization built into the probe for guidance. Another potential problem may arise with co-locating and registering the two optical modalities (OCT and a/LCI). The approach of using the same fiber source as illumination for both modalities will minimize this risk. The benchmark for success will be successful operation of both modalities in sequence without loss of performance in assessing the T-zone (less than 10% error vs. colpophotography) or detecting dysplasia (90% sensitivity / 90% specificity vs. histopathology).

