## Purpose of the Study

The purpose of this study is to develop an imaging probe that can be used to detect cervical dysplasia *in situ*. This probe will combine two imaging modalities, both types of low coherence interferometry (LCI), to examine the cervix on both the tissue and subcellular levels. The development of this probe will occur in two stages:

1. **Development of a multiplexed LCI (mLCI) endoscopic probe for mapping the epithelial types of the cervix.** This vaginal mLCI probe will obtain optical measurements in wide area scans of the cervix. These measurements can be used to create a map of the surface cells that distinguishes ectocervical epithelia, endocervical epithelia, and the squamocolumnar junction (T-zone) between them, which is the region where cervical dysplasia is most likely to occur.
2. **Development of an integrated probe that combines wide area cervical mapping with subcellular measurements of nuclear size to detect cervical dysplasia.** This combined probe will conduct wide area scans using optical coherence tomography (OCT - an updated technology similar to mLCI described above) to map the T-zone of the cervix. The mapping data will then be used to direct the locations for high resolution angle-resolved low coherence interferometry (a/LCI) nuclear morphology measurements to search for dysplasia at selected points. We have termed the combined technologies of OCT mapping and a/LCI nuclear sizing “**scanning a/LCI**.” In previous studies, a/LCI has proven highly accurate in detecting dysplastic lesions in Barrett’s esophagus patients via depth resolved nuclear morphology measurements. This study will adapt existing a/LCI technology to define the nuclear morphology characteristics of cervical epithelium.

The research studies described here will be preliminary studies to evaluate the performance of the LCI devices for detection of cervical dysplasia. The results from the small studies at Duke will help to optimize the function of the LCI instruments before completing larger studies with collaborators at Jacobi Medical Center. The devices will be studied in a larger subject population at Jacobi to determine how effectively they can distinguish the types of cervical epithelia and detect cervical dysplasia.

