### Subject Recruitment at Jacobi

Potential subjects will be informed of the study when they present to the clinic for a regular clinical care visit.

Jacobi will enroll up to 100 women for stage 1, in order to achieve the target number of 40 women who complete stage 1. For stage 2 of the study, up to 140 women will be recruited in order to enroll 70 participants in this cross-sectional study (50 HIV-negative participants and 20 HIV-positive participants). The goal distribution of participants in this study is approximately 14 women with normal histology, 21 women with CIN-1, 14 women with CIN-2 or CIN-2/3, 14 women with CIN-3, and 7 women with invasive cancer.

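### Stage 2 accuracy is read from an ROC curve and judged against 90%/90%, but no cut-off, depths or score are fixed and no internal validation is planned, so the result is likely to be optimistic

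*Combined protocol and SAP*

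**What the plan says.** The relevant text is in Data Analysis & Statistical Considerations, Stage 2, Data analysis for Jacobi site.

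- **Accuracy analysis.** Sensitivity and specificity come from one step: "an ROC curve will be created based on the a/LCI data and histological classification".
- **Outcome.** This is fixed: CIN-2 or worse against CIN-1 or normal.
- **Predictors.** These are given as "nuclear density and diameter at selected depths beneath the tissue surface". The depths are not named, and no score combining the two features is defined.
- **Regression.** "Repeated measures logistic regression models will be used to assess the association of histology with nuclear morphology characteristics". This describes an association analysis. The plan does not say whether the fitted model supplies the ROC score.
- **Repeated measures.** "A compound symmetric correlation matrix will be used to account for the repeated measures within subjects". This is stated for the regression. Nothing says whether the ROC unit is the woman or the measurement point.
- **Benchmark.** Success includes no loss of performance in "detecting dysplasia (90% sensitivity / 90% specificity vs. histopathology".

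Subject Recruitment at Jacobi gives the goal distribution as "14 women with normal histology, 21 women with CIN-1, 14 women with CIN-2 or CIN-2/3, 14 women with CIN-3, and 7 women with invasive cancer". Nowhere do the documents give a cut-off, a rule for choosing one, or any form of internal validation.

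**The concern.** A cut-off, a depth or a feature combination chosen because it separates the groups well in one sample will, on average, separate them less well in new women. If choice and scoring use the same data, the ROC gives apparent accuracy, which runs high. A device in the mid-80s would then look like a 90%/90% device more often than it should.

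The plan does not say where the rule will be chosen. That it will be chosen on the Jacobi women is an inference, for these reasons:

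- The Duke Stage 2 procedures include no biopsy. Histology comes only from the Jacobi visit.
- Background & Significance places earlier a/LCI dysplasia work in the esophagus, colon and trachea. It does not say that this work supplied cervical depths or a cut-off.
- Purpose of the Study says: "This study will adapt existing a/LCI technology to define the nuclear morphology characteristics of cervical epithelium". The cervical features are therefore still to be defined.

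At stake is the figure carried forward. Purpose of the Study says the devices go to a "larger subject population at Jacobi to determine how effectively they can distinguish the types of cervical epithelia and detect cervical dysplasia", so this is the accuracy estimate on which later work would build.

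**Working it through.** **Inputs from the documents.** CIN-2 or worse: 14 + 14 + 7 = 35. CIN-1 or normal: 14 + 21 = 35. Total 70, which matches the stated Stage 2 target. No power or precision calculation is given for Jacobi Stage 2, so there is no planned figure to reproduce beyond this sum.

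**Assumptions not in the documents.** Binormal marker values with equal variances; cut-off at the maximum Youden index (sensitivity + specificity − 1); number of markers; points per woman and their correlation.

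**Step 1: what the benchmark requires.** 31/35 = 88.6% and 32/35 = 91.4%, so at least 32 of 35 must be correct in each group.

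**Step 2: cut-off fixed beforehand, one result per woman.** The chance of meeting both is P(X ≥ 32)², with X ~ Binomial(35, p):

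- p = 0.80: 0.0605² = 0.0037
- p = 0.85: 0.2088² = 0.0436
- p = 0.90: 0.5310² = 0.2819

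**Step 3: cut-off chosen on the same women, one marker, one result per woman** (simulation, 20,000 replicates, ties broken at random).

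| True sensitivity/specificity | Cut-off fixed beforehand | Youden cut, same data | Any qualifying cut accepted |
|---|---|---|---|
| 80%/80% | 0.4% | 1.0% | about 1.3% |
| 85%/85% | 4.4% | 9.3% | about 12% |
| 90%/90% | 28% | 42% | about 53% |

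At true 85%/85% the mean apparent values are 87.7%/87.6%. The same rule gives 84.0%/83.9% in new women, so the optimism is 87.7 − 84.0 = 3.7 points for sensitivity and 87.6 − 83.9 = 3.7 for specificity. Breaking ties toward sensitivity gives 89.3%/86.0% against 85.6%/82.2%, again about 4 points each.

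**Step 4: several points per woman, point-level ROC, true 85%/85%** (8,000 replicates, all points in a woman of one class).

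| Points per woman, correlation | Fixed | Youden, same data | Optimism (points) |
|---|---|---|---|
| 2, 0.3 | 2.8% | 5.4% | 2.5 |
| 2, 0.8 | 4.7% | 8.9% | 2.7 |
| 3, 0.5 | 1.5% | 3.1% | 2.0 to 2.1 |
| 5, 0.3 | 0.3% | 0.6% | 1.5 |
| 5, 0.8 | 2.1% | 3.9% | 1.8 to 1.9 |

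Allowing both classes within a woman gave 2% to 3%, against 0.6% to 1.2% with a fixed cut-off, and about 2 points of optimism.

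**Step 5: several predictors combined on the same data.** The plan does not state this but leaves it open. A linear discriminant on 4, 6 or 10 predictors, one of them informative, with one result per woman and a Youden cut gives 14%, 18% and 27% at true 85%/85%.

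**Step 6: does internal validation remove it?** One marker, one result per woman, true 85%/85%, every selection step repeated in each fold or resample. The chance of meeting both targets is:

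- 7-fold cross-validation, class-balanced by woman: 3.2% (means 83.7%/83.9%)
- leave-one-woman-out: 6.0% (means 85.1%/85.4%)
- bootstrap optimism correction: 5.3%

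These bracket the 4.4% of a fixed cut-off. The 7-fold means sit close to the 84% achieved in new women; leave-one-out runs about 1 point high.

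**Step 7: precision.** The Clopper-Pearson 95% interval for 32/35 is 76.9% to 98.2%.

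**The case against.** The strongest reply is that this is a first cervical data set, described as preliminary and as early feasibility work, and that an exploratory ROC is the ordinary analysis for it. The 90%/90% target follows a discussion of registering the two optical modalities and can be read as an engineering goal for the integrated probe. No hypothesis test or go/no-go rule is attached. This stands and limits the weight of the point. It does not remove it, because the target is still a numerical accuracy against histopathology.

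Second, same-data selection is inferred. One might cite Stage 1, where algorithms are developed on accruing maps, but that text describes cluster analysis for another device and task, so it adds little. The inference rests on the absence of any other cervical a/LCI data with histology. If a locked rule exists, one sentence closes the matter.

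Third, the effect is modest. The regression expects repeated measures, so a point-level ROC is at least as plausible as one result per woman, and the absolute excess is then often only 1 to 4 percentage points. Even 4 points of optimism is below one standard error for 35 women: √(0.85 × 0.15 / 35) = 6.0 points. This also stands: imprecision is the larger problem. But optimism has a direction, and a confidence interval placed around an apparent value does not remove it.

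Fourth, locking a numerical cut-off beforehand has little empirical basis if no cervical data exist. That is fair, and it favors the internal-validation route.

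**Conclusion.** The concern holds. As written, the plan most naturally yields apparent accuracy and compares it with 90%/90%. For a single marker at true 85%/85%, the optimism is about 4 points with one result per woman and 1.5 to 2.7 points with a point-level ROC. The chance of seeming to meet the benchmark is roughly double that of a fixed cut-off in either case. It is larger only if several predictors are combined on the same data. A true 80%/80% device with one marker rarely appears to pass (about 1%), so the problem is confined mainly to devices in the mid-80s. These sizes depend on the binormal model, the Youden rule and the 35/35 split; the direction does not. The compound symmetric structure deals with correlation within women, not with this optimism. It should be fixed, but the harm is a misleading accuracy figure in later work, not a risk to participants.

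**What to change.** Add a short paragraph to the Stage 2 Jacobi analysis.

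1. State the ROC unit (woman or point), the candidate features and depths, how they form one score, and the rule for choosing the cut-off.
2. Report the benchmark sensitivity and specificity as woman-level cross-validated or bootstrap optimism-corrected values. Keep all points from one woman in the same fold and repeat every selection step inside each fold or resample. Class-balanced folds are preferable to leave-one-woman-out.
3. Give 95% confidence intervals by resampling women. Label the apparent ROC as descriptive, and read 90%/90% together with its interval.
4. Alternatively, if the sponsor already has a basis for a cervical rule, fix features, depths, unit and cut-off in writing before a/LCI data are linked to histology.

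**Cost.** No new women or visits: some text and programming, possibly outside the named software (JMP Version 9). Reported accuracy will be lower, and a good device will miss the point targets more often. With one marker and one result per woman, a true 90%/90% device meets both 42% (Youden cut) to 53% (any qualifying cut) of the time as planned. This falls to 28% with a fixed cut-off and 24% to 30% after cross-validation or bootstrap correction. With 3 points per woman and correlation 0.5, the figures are 37%, 27% and 22% (7-fold). For that reason 90%/90% should not serve as a bare pass/fail on point estimates.

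### Stage 2 tests several nuclear features at unspecified depths against p<0.05 with no joint test or multiplicity rule, so the chance of a false association claim exceeds 5% by an amount that depends on choices the plan leaves open

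*Combined protocol and SAP*

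**What the plan says.** The Stage 2 part of Data analysis for Jacobi site says "Repeated measures logistic regression models will be used to assess the association of histology with nuclear morphology characteristics". The outcome is split into CIN-2 or worse against CIN-1/normal. The device predictors are "nuclear density and diameter at selected depths beneath the tissue surface". On adjustment it says "Potential confounders will be adjusted for, including age, type of epithelium (i.e. metaplastic, squamous), infections if found, menstrual cycle timing, and sexual behaviors", and on clustering "A compound symmetric correlation matrix will be used to account for the repeated measures within subjects". The decision rule is one sentence: "P-values associated with type I error rates of less than 0.05 will be considered statistically significant in this study".

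The section does not give the number of depths or how they are chosen. It does not say whether the features enter one model or several, how the covariates are coded, or how many matched readings each woman contributes. It names no primary feature, joint test or correction for multiple tests. Its benchmark for success is a separate matter: 90% sensitivity and 90% specificity against histopathology, with T-zone error below 10%.

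Subject Recruitment at Jacobi gives the approximate target mix: "14 women with normal histology, 21 women with CIN-1, 14 women with CIN-2 or CIN-2/3, 14 women with CIN-3, and 7 women with invasive cancer".

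**The concern.** Depths is plural, so two features give at least four nuclear terms. A blanket 0.05 rule with no named primary term leaves the analyst free to report any of them as significant. The error rate attached to the statement that nuclear morphology is associated with CIN-2 or worse is then no longer 5%. The more depths are tried, the further it drifts. A false finding could also steer later work towards the wrong feature or depth.

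There is a loss in the other direction too. Readings at neighbouring depths overlap, so mutually adjusted tests can each miss an effect that is strong when the terms are taken together.

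A second question is whether the model can be fitted at all when the device works well, since the adjusted model is large for the number of women with CIN-2 or worse.

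**Working it through.** **Inputs from the documents**
- Threshold: 0.05 (sidedness not stated; two-sided assumed).
- Women with CIN-2 or worse: 14 + 14 + 7 = 35. Others: 14 + 21 = 35. Total 70, which matches the stated target. The documents give no power calculation or overall error figure to reproduce.

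**Assumed, because not stated**
- Depths: 2, 3 or 4, giving k = 4, 6 or 8 nuclear terms.
- Covariate terms: 6 to 8 for the five named kinds.
- Readings per woman: one, with a check at three.

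**Step 1. Independent tests.** The chance of at least one p<0.05 is 1 − 0.95^k: 0.1855 (k = 4), 0.2649 (k = 6), 0.3366 (k = 8).

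**Step 2. Correlated separate tests.** Correlation between features lowers the figure but does not bring it to 5%:

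| Correlation | k = 4 | k = 6 | k = 8 |
|---|---|---|---|
| 0.5 | 15.5% | 20.7% | 24.9% |
| 0.7 | 12.9% | 16.5% | 19.1% |
| 0.9 | 9.5% | 10.8% | 11.9% |

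Simulated separate logistic models with six covariate terms, 35 against 35 women, gave 9 to 39%.

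**Step 3. One joint adjusted model.** Null logistic fits, 35 against 35 women, 6 or 8 covariate terms, correlation 0 or 0.5, 1000 runs per setting:
- k = 4: 20.5 to 22.9%
- k = 6: 30.3 to 35.9%
- k = 8: 40.7 to 45.5%

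Further runs with six covariate terms took the lower ends to 15% for two or three depths and 37% for four. Simulation error near 22% is √(0.22 × 0.78 / 1000) = 1.3 points. The joint-model rates mostly lie above those in Step 1, so small-sample error adds to multiplicity. Correlation gives little protection here, because mutual adjustment removes the shared part of the features.

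**Step 4. Repeated readings.** With 70 women, three readings each, an exchangeable working correlation, six covariate terms and 300 runs per setting, the rates were 22 to 23% (k = 4), 29 to 33% (k = 6) and 38 to 47% (k = 8). Simulation error near 30% is √(0.3 × 0.7 / 300) = 2.6 points. The excess is therefore not an artefact of assuming one reading.

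**Step 5. A joint test instead.** Across the null runs, a joint score test of all nuclear terms rejected in 4 to 9%. A joint likelihood-ratio test rejected in 8 to 16%.

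**Step 6. Separation.** One normally distributed feature that reaches 90/90 puts the groups 2 × 1.2816 = 2.563 SD apart. With one reading per woman, complete or quasi-complete separation occurred in 38% of trials with 10 terms and about 40 to 60% with 11 to 13 terms (one set of runs reached 64% at 13). With two readings it fell to 2 to 4%, and with three to about 0. At 2.0 SD with one reading it was about 5% (10 terms) and 20% (14 terms).

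**The case against.** The strongest reply is that the plan is under-specified rather than wrong. It does not say that each feature at each depth is judged on its own p-value. It speaks of models in the plural and leaves open joint terms, separate models or a combined score. This stands, and it is why only ranges can be given. It does not remove the problem, because a blanket 0.05 rule permits single-term claims and both joint and separate models exceed 5%. A single score fixed in advance would avoid the excess, but none is named.

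A reader might infer that a useless device has this chance of being declared successful. The documents do not support that, because success rests on the 90/90 and T-zone benchmarks and not on a p-value.

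A reader might also infer that the model is simply too large and will fail if the device is good. With 10 to 16 terms there are 35/10 = 3.5 down to 35/16 = 2.2 women with CIN-2 or worse per term. That count is fair for covariates recorded once per woman, such as age. It is too pessimistic for nuclear features and epithelium type, which vary by site. The plan is for repeated measures, and separation is mainly a one-reading result.

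Finally, the work is described as preliminary. That limits the consequence, but the plan still states a significance threshold and intends to use it.

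**Conclusion.** The point holds as a gap in the decision rule. With no information in the nuclear features, the chance of at least one significant term is about 15 to 35% for two or three depths in one joint adjusted model, about 37 to 46% for four depths, and about 9 to 39% for separate models. The position within each range depends on the number of depths and the correlation between them. All figures rest on assumed depths, assumed covariate coding, normally distributed features and, except in the check in Step 4, one reading per woman. The lowest figure is still almost twice 5%.

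What is at risk is the association claim and the selection of features and depths. The sensitivity and specificity benchmark is untouched. Non-convergence is a secondary risk, real only if most women contribute a single matched reading, which the documents neither state nor rule out. The plan should be changed before analysis; the design need not be.

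**What to change.** 1. Name the depths before any outcome data are seen.
2. Make one joint score test of all nuclear density and diameter terms, clustered by woman, the only association claim at two-sided 0.05. Specify the score test and not the likelihood-ratio test, given the rejection rates in Step 5.
3. Label individual feature-by-depth p-values descriptive unless the joint test passes.
4. Name Firth-type penalised estimation, with variance clustered by woman, as the fallback if the planned compound-symmetric model does not converge. It should not replace the planned model otherwise.

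The cost is a few sentences in the analysis section and a different test call, with no extra women or procedures. Single-feature claims become harder to make, and the joint test may still run slightly above 5%. Cutting the covariate list would also help the fit, but it trades against control of confounding, so it is not part of this fix.

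### The Stage 2 Jacobi 90/90 benchmark has no interval or lower limit, so at about 35 women per group most passing results would not establish 90% and a miss would not show that the device falls short of it

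*Combined protocol and SAP*

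**What the plan says.** All references are to the combined protocol and SAP.

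- **Benchmark.** Data Analysis & Statistical Considerations, Stage 2, Data analysis for Jacobi site: "The benchmark for success will be successful operation of both modalities in sequence without loss of performance". Performance in detecting dysplasia is then put at "90% sensitivity / 90% specificity vs. histopathology", next to a limit on T-zone error.
- **Source of the two rates.** Same section: "an ROC curve will be created based on the a/LCI data and histological classification". No cut-off is fixed in advance, and no rule is given for choosing one.
- **Disease definition.** Same section: "The outcome variable will be dichotomized as “CIN-2 or worse” vs. CIN-1/normal". Invasive cancer therefore counts as a positive.
- **Numbers.** Subject Recruitment at Jacobi: "up to 140 women will be recruited in order to enroll 70 participants in this cross-sectional study". The mix is introduced with "The goal distribution of participants in this study is approximately" and comprises "14 women with normal histology, 21 women with CIN-1", then "14 women with CIN-2 or CIN-2/3, 14 women with CIN-3, and 7 women with invasive cancer".
- **What is absent.** No interval, minimum lower limit, precision statement or unit of analysis is given for sensitivity and specificity at Jacobi. The 0.05 level applies to p-values and is not tied to the benchmark. The Duke sections do state a precision (10%).

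**The concern.** A numerical success line is compared with two observed proportions, each from about 35 women, and nothing in the plan expresses their uncertainty. A pass could be read as demonstrated 90/90 accuracy when the data allow considerably less. A miss could be read as device failure when the device truly performs at 90/90. If the cut-off is chosen from the same data, the observed rates also tend to flatter the device. Finally, the benchmark is for detecting dysplasia, but one fifth of the planned positives are invasive cancers.

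**Working it through.** **Inputs.** From Subject Recruitment at Jacobi: positives 14 + 14 + 7 = 35, of which 7 (20%) are cancers; negatives 14 + 21 = 35; total 70, which agrees with the stated target. From the Stage 2 Jacobi analysis section: 90% for each rate. The plan gives no power or precision figure for this benchmark, so there is none to reproduce.

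**Assumptions added here.** One result per woman, exactly 35 per group, and sensitivity and specificity independent.

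**1. Lowest passing count.** 0.90 × 35 = 31.5, so 32 are needed: 32/35 = 91.4% passes and 31/35 = 88.6% does not.

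**2. What a pass shows.** Exact (Clopper-Pearson) two-sided 95% intervals:

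| Observed | Estimate | Lower limit | Upper limit |
|---|---|---|---|
| 32/35 | 91.4% | 76.9% | 98.2% |
| 33/35 | 94.3% | 80.8% | 99.3% |
| 34/35 | 97.1% | 85.1% | 99.9% |
| 35/35 | 100% | 90.0% | 100% |

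For 35/35 the lower limit is 0.025^(1/35) = 0.900. Only a perfect result reaches 90%.

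**3. Chance of passing with a pre-set cut-off.** For one rate, P(X ≥ 32) with X ~ Bin(35, p); for both, its square.

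| True sensitivity and specificity | One rate | Both |
|---|---|---|
| 85% | 0.209 | 0.044 |
| 90% | 0.531 | 0.282 |
| 95% | 0.904 | 0.818 |

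At a true 90/90 the chance of a miss is 1 − 0.282 = 0.718, about 72%.

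**4. Chance of passing when the cut-off comes from the same ROC data.** Simulation with 35 + 35 women, normal scores of equal variance and separation 2 × Φ⁻¹(p). A pass means that some cut-off gives at least 32/35 on both rates. At a true 90/90 the pass rate is about 54%, so the miss rate is about 46% to 47% across runs. At a true 85/85 the pass rate is about 12%, against 4% with a pre-set cut-off. Choosing the cut-off this way therefore makes the observed rates optimistic.

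**5. Sensitivity of step 3 to its assumptions.** Other splits of the 70 women (from 20/50 to 42/28) give miss rates of 58% to 73%. Two or three results per woman, treated naively as independent, give 64% and 73%. Accepting 31/35 as 90% by rounding gives 1 − 0.731² = 47%.

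**6. Invasive cancers.** CIN-2 and CIN-3 make up 14 + 14 = 28 positives. With all 7 cancers detected:

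- 24/28 = 85.7% becomes 31/35 = 88.6%: below the line both ways.
- 25/28 = 89.3% becomes 32/35 = 91.4%: below the line alone, above it pooled.
- 26/28 = 92.9% becomes 33/35 = 94.3%: above the line both ways.

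The verdict changes at one count, by about 2 percentage points. If true CIN-2/3 sensitivity were 85% and every cancer were detected, the chance of meeting the sensitivity part would be P(Bin(28, 0.85) ≥ 25) = 37.7% pooled, against P(Bin(28, 0.85) ≥ 26) = 18.7% on CIN-2/3 alone.

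**The case against.** The strongest reply is that the protocol describes this work as preliminary (Purpose of the Study) and as early feasibility (Potential Benefits), attaches no go/no-go decision to the benchmark, and places it at the end of a paragraph on co-registration risks. That stands in part: a claim of 90/90 accuracy after a pass is a foreseeable reading, not one the documents commit to. But Purpose of the Study also gives the larger Jacobi population the task of determining how effectively the devices detect dysplasia. The analysis section sets out to determine sensitivity and specificity, and this is the only numerical criterion for detecting dysplasia.

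Several stronger readings are tempting, and the documents do not support them:

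- **That any pass leaves 77% open.** This is true only of 32/35; the lower limits rise to 81%, 85% and 90% for the higher counts.
- **That a true 90/90 device misses 72% of the time without qualification.** That needs a pre-set cut-off, whereas the plan takes the rates from the study's own ROC curve. It also needs one result per woman, whereas data are collected at several locations and modelled as repeated measures. The 35/35 mix is itself only an approximate goal.
- **That the cancers drive the result.** The definition is stated openly and the verdict changes at one count only.

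It is also fair to say that a conclusion worded as consistent with 90/90 would be too loose: 28/35 = 80% has an exact interval of 63% to 92% and would qualify.

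**Conclusion.** The point holds in limited form. No interval or lower limit accompanies the benchmark, and at the goal mix the passing counts from 32/35 to 34/35 have lower limits of 77% to 85%. Most passes therefore do not establish 90%. Near a true 90/90 the outcome owes much to chance: a miss about 72% of the time with a pre-set cut-off, or about 46% to 47% with a cut-off from the same ROC data under an equal-variance binormal model. The second route also raises the pass rate of an 85/85 device from about 4% to about 12%. These figures rest on one result per woman, 35 per group and independence. The plan states neither the cut-off rule nor the unit, so none of the pass or miss rates is the plan's actual operating characteristic. The cancer issue is secondary. A reader might infer that 70 women are too few or that 90/90 is the wrong target; neither follows, since the defect is in what the rule allows to be concluded. It should be corrected before the analysis.

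**What to change.** Keep 70 women and the 90/90 target, and change the Stage 2 Jacobi analysis text as follows.

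1. State the unit of analysis for sensitivity and specificity, and how the cut-off is obtained.
2. Report both rates with woman-level 95% intervals. Use exact intervals if there is one result per woman and a pre-set cut-off. Use a bootstrap over women if there are several sites per woman or the cut-off comes from the same ROC data; in the latter case repeat the cut-off selection in every resample.
3. Base the conclusion on the interval: give the point estimate and say which values, those below the lower limit, are excluded. A pass is then not reported as established 90/90 accuracy, and a miss whose interval includes 90% is not reported as device failure.
4. Report sensitivity for CIN-2/3 separately from invasive cancer, as a secondary result.

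The 28% chance of passing should not be written into the plan unless a cut-off and a unit are pre-set, because it would otherwise describe a method that the plan does not commit to.

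The cost is SAP wording and a few table rows, with no new data. The downside is a more modest claim and wide intervals in the strata: 7/7 cancers has an exact lower limit of only 59%.
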